Official Title: An Intraoperative Guidance Platform for Radio Frequency Ablation

NCT number: NCT04152343

Document Type: Statistical Analysis Plan

Date of the Document: July 10, 2018

PRINCIPAL INVESTIGATOR:

[name]

Department of Radiology

Section of Interventional Radiology

Dartmouth-Hitchcock Medical Center

[name]

[name]

[contact]

Email: [contact]

As noted in the protocol, the following Statistical Analysis Plan is referenced in the protocol (page 9). The following was obtained from the study SF19108 clinical protocol v29July2019, pages 13-18, Section 6.0 Statistical Plan

6 Statistical Plan

6.1 *Population Size*

Fifty two (52) patients will be recruited in the study, anticipating that up to 4 patients might drop out from the study, leaving a total of 48 patients. Based on prior statistics from [name] clinic, approximately 30% of patients have more than one tumor which is treated. Assuming that 30% of the patients have two tumors,

recruitment of 48 subjects will yield 62 treated individual tumors which will be analyzed. A population of 62 analyzed tumors provides a sufficient statistical power for the outcomes the trial is designed to estimate, given reasonable hypotheses on the effect size that the PGP will result in, as discussed next.

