6.3.1 Power for technical success

If the analysis of the above one-sided hypothesis test for p_{RFA} for an ablative margin of 3mm is conducted using Fisher's exact test, then with a sample-size of 62 lesions and allowing a type I error of 0.05, we can detect a value of $p_{RFA} > 0.161$ with 80% power. That is, the minimal detectable p_{RFA} difference is 0.103. Subgroup analyses (e.g., based on treated tumor size) will require larger effect sizes to retain the same level of power. However, the study is only intended to be powered for the primary analysis.

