Patients are enrolled in the study over a 2-year period. Therefore, if every patient was followed up for 2-years, the study would be 4-years long. We propose a statistical analysis plan which will allow estimating the clinical performance of the PGP at any point after the initial recruitment phase of 2 years – with increasing accuracy as the analysis approaches the 4-year mark, having access to 2-year follow up data for each patient who entered the study.

The analysis will be as follows: the investigators will check the status of patients every 6-months (data may be available every 3-months for some patients but to be safe we only assume 6-month interval data will be available) and essentially impute future status from patients' prior status. The imputations will be automatically performed by a Bayesian analysis, which assigns an unknown parameter to each participant's 6-monthly future status, through 2-years of follow-up.

The data for each patient is a 5-item multinomial random variable indicating whether they experienced recurrence before 6-months, between 6 and 12 months, between 12 and 18 months, between 18 and 24 months, or survived recurrence-free to 24 months and a covariate for the size of tumor. The four values of the multinomial outcome variable are (1,0,0,0,0) for recurrence before 6 months, (0,1,0,0,0) for recurrence between 6 and 12 months, (0,0,1,0,0) for recurrence between 12 and 18 months, (0,0,0,1,0) for recurrence between 18 and 24 months, and (0,0,0,0,1) for no recurrence in the 24-months follow up period.

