6.4.1 Notation for multinomial (discrete-valued) outcome

Let $y_{ij} = (y_{ij0}, y_{ij1}, y_{ij2}, y_{ij3})$ denote the multinomial outcome for the i th patient as assessed by the j th rater ($j = 1, 2$) and x_i denotes the tumor size for the i th of $n = 62$ lesions analyzed in the study.. The covariate x_i can be the actual size or a vector of categorical variables indicating whether the tumor is in that size category or the excluded baseline category (e.g., medium versus small, large versus small). If tumor-size is not included in the analysis, x_i is the empty set.

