6.4.2 Model for multinomial outcome: generalized logistic regression

The distribution of y_i is multinomial with five categories:

$$y_i | \theta_i \sim \text{Multinomial}_5(1, \theta_i)$$

where $\theta_i = (\theta_{i0}, \theta_{i1}, \theta_{i2}, \theta_{i3}, \theta_{i4})$ is the vector of probabilities associated with the five possible outcomes for patient i . Models for multinomial outcomes are characterized by the way in which the elements of θ_i are mapped to the predictors. One commonly used specification is generalized logistic regression in which each component of θ_i is compared to all other components through a logit link function by supposing:

$$\theta_{ik} = \lambda_{ik} / (\lambda_{i0} + \lambda_{i1} + \lambda_{i2} + \lambda_{i3} + \lambda_{i4})$$

and $\log(\lambda_{ik}) = \gamma_k + \beta x_i$ for $k = 0, \dots, 4$. A key feature of this specification is that the Bayesian software package JAGS will impute any y_{ik} whose value is missing. To implement this feature any values of y_{ik} that are missing will be represented as NA in the analytic data set. We note that the above specification assumes the proportional odds assumption that the effects of all terms other than γ_k does not depend on k holds. This is an assumption whose legitimacy can be tested empirically.

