6.4.4 Evaluation of hypothesis test and other summaries of the posterior distribution

We wish to average the 2-year survival probability across the study patients, given by

$$q_{\text{RFA}} = 1 - n^{-1} \sum_{i=1}^n \theta_{i4}$$

where based on the above generalized logit model the probability of clinical success at 2-years for patient i is given by

$$\theta_{i4} = \frac{\exp(\gamma_4 + \beta x_i)}{\exp(\gamma_0 + \beta x_i) + \exp(\gamma_1 + \beta x_i) + \exp(\gamma_2 + \beta x_i) + \exp(\gamma_3 + \beta x_i) + \exp(\gamma_4 + \beta x_i)}$$

The posterior probability of clinical success, $\Pr(q_{\text{RFA}} < q_{\text{base}} | y_1, \dots, y_n, x_1, \dots, x_n)$, is then determined by evaluating q_{RFA} for a large number of draws from the posterior distribution of the model parameters and evaluating the Monte-Carlo average

$$\Pr(q_{\text{RFA}} < q_{\text{base}} | y_1, \dots, y_n, x_1, \dots, x_n) \cong n^{-1} \sum_{j=1}^{n_{\text{sim}}} I(q_{\text{RFA}}^j < q_{\text{base}})$$

where q_{RFA}^j denotes the value of q_{RFA} computed on the j th of n_{sim} draws of the model parameters from their joint posterior distribution. The mean, standard deviation, and 95% interval estimates of q_{RFA} will be similarly determined.

Because the chance of clinical success likely varies continuously with tumor size, we can substitute the mean tumor size for the benchmark population in [4] for x_i to essentially control for tumor size. Alternatively, we may substitute x_i with the corresponding small, medium, and large tumor size subgroup mean and in so-doing evaluate the posterior probability with closer control for the tumor size distribution. For the subgroup analyses that compare the performance of RFA-GP on the small, medium and large tumor

subgroups we may estimate $\Pr(q_{\text{RFA}} < q_{\text{base}} \mid \text{size} = s, y_1, \dots, y_n, x_1, \dots, x_n)$ separately for each subgroup $s \in \{\text{small, medium, large}\}$.

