6.4.5 Technical Note: Alternative computational strategy

If there are any technical challenges getting the generalized logistic regression model to run in JAGS (the Bayesian statistical software) with missing values for some of the multinomial outcomes, we will use the continuation-ratio model defined by the logits of the events: recurrence-free versus recurrence at 6 months, recurrence-free versus recurrence at 12 months given recurrence-free to 6 months, recurrence-free versus recurrence at 18 months given recurrence-free to 12 months, and recurrence-free versus recurrence at 24-months given recurrence-free to 18-months. Thus, each successive analysis is conditioned on a reduced set of subjects. It can be shown that the multinomial likelihood function decomposes into separate likelihood functions for each of the above conditional contrasts. Importantly, it is computationally easier to estimate separate logistic regression models as opposed to simultaneously needing to estimate the generalized logit model.

The probabilities estimated by the respective logits of the continuation ratio model are given by:

$$\begin{aligned}\eta_{i0} &= \theta_{i1} + \theta_{i2} + \theta_{i3} + \theta_{i4} \\ \eta_{i1} &= (\theta_{i2} + \theta_{i3} + \theta_{i4}) / (\theta_{i1} + \theta_{i2} + \theta_{i3} + \theta_{i4}) \\ \eta_{i3} &= (\theta_{i3} + \theta_{i4}) / (\theta_{i2} + \theta_{i3} + \theta_{i4}) \\ \eta_{i4} &= \theta_{i4} / (\theta_{i3} + \theta_{i4})\end{aligned}$$

or equivalently

$$\begin{aligned}\theta_{i0} &= 1 - \eta_{i1} \\ \theta_{i1} &= \eta_{i1}(1 - \eta_{i2}) \\ \theta_{i2} &= \eta_{i1}\eta_{i2}(1 - \eta_{i3}) \\ \theta_{i3} &= \eta_{i1}\eta_{i2}\eta_{i3}(1 - \eta_{i4}) \\ \theta_{i4} &= \eta_{i1}\eta_{i2}\eta_{i3}\eta_{i4}\end{aligned}$$

Because there is a one-to-one relationship between the sets of probabilities, following estimation of the separate logistic regression models we simply need to multiply the necessary probabilities together to recover the probabilities for the multinomial model and thus evaluate the hypothesis test for clinical success.

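### The 62 lesions come from 48 patients, yet both 80% power statements and the recurrence model treat them as independent, and the index i means both patient and lesion; the effect is modest

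*SAP*

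**What the plan says.** SAP Section 6.1 starts from 52 recruits, allows for 4 drop-outs, assumes two tumors in 30% of the remaining 48 patients, and concludes that "recruitment of 48 subjects will yield 62 treated individual tumors which will be analyzed".

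The lesion count is then the sample size for both primary outcomes. For technical success, Section 6.3.1 uses an exact test, "then with a sample-size of 62 lesions and allowing a type I error of 0.05", and gives 80% power at a success rate of 0.161 against the benchmark 0.0577. For recurrence, Section 6.4.6 gives 80% power with 62 lesions at a rate of 0.105 against 0.2217, and calls the calculation illustrative.

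The unit is not consistent in the recurrence model:

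- Section 6.4: "The data for each patient is a 5-item multinomial random variable indicating whether they experienced recurrence before 6-months".
- Section 6.4.1: the outcomes "denote the multinomial outcome for the i th patient as assessed by the j th rater", but the covariate in the same sentence "denotes the tumor size for the i th of $n = 62$ lesions analyzed in the study".
- Section 6.4.2: the probability vector "is the vector of probabilities associated with the five possible outcomes for patient" i.
- Section 6.4.4: "We wish to average the 2-year survival probability across the study patients", with a sum that runs to n.

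The linear predictor in Section 6.4.2 contains only a category intercept and tumor size, and Section 6.4.3 gives priors for those two alone. The fallback in Section 6.4.5 ("we will use the continuation-ratio model defined by the logits of the events") adds no patient term.

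**The concern.** Two lesions in one patient share a liver and a follow-up schedule, so a positive correlation between their outcomes is plausible. If it is present, 62 lesions carry less information than 62 independent observations. The interval for the recurrence probability q_RFA is then too narrow, as is the interval for p_RFA from the simple one-sample test in Section 6.3, and a flat 80% power is optimistic.

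The double use of i matters whatever the correlation is. A patient with one recurrent and one recurrence-free lesion has two outcomes, and the statistical plan does not say how they enter a model that gives each patient one.

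Recurrence is the more exposed outcome, because its illustrative rule uses nearly all of the 5% level, whereas the technical-success rule uses about half of it.

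**Working it through.** **Inputs.** From the SAP: 48 patients, 30% with two tumors (6.1); 62 lesions and a one-sided level of 0.05 (6.3.1, 6.4.6); 0.0577 against 0.161 (6.3, 6.3.1); 0.2217 against 0.105, and the less conservative benchmark of 24.1% (6.4, 6.4.6). Assumed: within-patient correlation rho, shown at 0.1, 0.3 and 0.5. The benchmarks are taken as written. The tumor-size weighting of Section 6.2 is left out, because its effect cannot be computed from the documents.

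**Step 1: lesion count.** 48 × 1.3 = 62.4. In whole patients, 34 × 1 + 14 × 2 = 62.

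**Step 2: the plan's power.** A one-sample exact binomial test with n = 62 independent lesions gives:

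- Technical success: reject at 8 or more. Level 0.026 at 0.0577, power 0.802 at 0.161.
- Recurrence: reject at 8 or fewer. Level 0.048 at 0.2217, power 0.801 at 0.105.

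The normal approximation (0.879 and 0.779) and the arcsine method (0.850 and 0.810) match the two statements less well. The 80% figures therefore contain no design effect.

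**Step 3: design effect.** With 28 of the 62 lesions in pairs, the design effect is 1 + (28/62) × rho. The factor for interval width is its square root.

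**Step 4: same cut-offs with correlated pairs.** For a rate p, both lesions of a pair have the event with probability p² + rho × p(1 − p). Exact convolution of 34 single lesions and 14 such pairs gives:

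| | rho 0 | 0.1 | 0.3 | 0.5 |
|---|---|---|---|---|
| Design effect | 1 | 1.045 | 1.135 | 1.226 |
| Interval width factor | 1 | 1.022 | 1.066 | 1.107 |
| Recurrence, level vs 0.2217 | 0.048 | 0.052 | 0.060 | 0.067 |
| Recurrence, level vs 0.241 | 0.023 | 0.025 | 0.030 | 0.035 |
| Recurrence, power at 0.105 | 0.801 | 0.796 | 0.788 | 0.781 |
| Technical, level vs 0.0577 | 0.026 | 0.029 | 0.034 | 0.040 |
| Technical, power at 0.161 | 0.802 | 0.796 | 0.785 | 0.774 |

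The technical-success level reaches 5% only near rho 0.9. Against 24.1% the recurrence rule stays below 5% even at rho 1 (0.049).

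**Step 5: can clustering be handled at this size?** The check was a test of a single 2-year proportion against 0.2217, with complete follow-up. It used a patient-clustered variance, a 48/47 correction, t on 47 degrees of freedom and the logit scale. Exact enumeration at rho 0, 0.1, 0.3 and 0.5 gives a level of 0.043, 0.044, 0.046 and 0.046, and power at 0.105 of 0.775, 0.750, 0.706 and 0.667. On the proportion scale the level is about 0.08 throughout, so the scale must be stated.

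**Step 6: sparse data.** At q = 0.105, 62 × 0.105 = 6.5 recurrences are expected. If they fall evenly over four 6-month intervals (an assumption), each interval has probability 0.02625 per lesion. For independent lesions with complete follow-up, the chance that at least one interval is empty is 4(0.97375)^62 − 6(0.9475)^62 + 4(0.92125)^62 − (0.895)^62, which is about 0.58. An unpenalized logit for an empty interval is not finite.

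**Step 7: one lesion per patient (n = 48).** Recurrence: reject at 5 or fewer, level 0.030, power 0.609. Technical success: reject at 7 or more, level 0.020, power 0.672.

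**The case against.** The effect is small. At rho 0.5, a value that nothing in the documents supports, power falls by about two to three percentage points at unchanged cut-offs. Both power statements are hedged: Section 6.3.1 is conditional on the test used, and Section 6.4.6 says that it is illustrative. The analyzed number is clear at 62 lesions, so part of the index problem is editorial. Sections of SF19108 that the protocol only cross-references may define the unit. All of this stands and limits the weight of the point.

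Three stronger readings are tempting, and the documents do not support them.

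- *The primary recurrence analysis exceeds its 5% level.* The figures of 0.052 to 0.067 belong to the illustrative binomial rule against 0.2217, which the SAP calls its most conservative benchmark. The planned decision is a posterior probability (Section 6.4.4) without a stated cut-off, so its level cannot be computed.
- *The SAP ignores clustering altogether.* The Rasch model in Section 6.3 has a subject effect. It is optional, is introduced for repeated ratings, and does not say whether two lesions of one subject share it. For technical success the point is therefore firm only for the simple one-sample test.
- *Clustering cuts recurrence power to about 0.67.* Moving the cut-off from 8 to 7 to hold the level gives about 0.67, but that cut-off gives only 0.676 with independent lesions. Most of the drop comes from the discreteness of the test.

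**Conclusion.** The point holds, and its size is modest. The SAP as given derives 62 lesions from 48 patients, powers both primary outcomes as if lesions were independent, and specifies a recurrence model with no patient term and an index with two meanings.

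Under an assumed correlation of 0.1 to 0.5, the recurrence interval should be about 2% to 11% wider, and 80% becomes about 0.77 to 0.80 at the same cut-offs. Only the illustrative recurrence rule against 0.2217 goes above 5%. For technical success the level stays at or below 0.040 over this range, so a clarified unit and restated power are enough. A new test is not needed there to protect the level.

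These sizes rest on the assumed correlation, the 34/14 split from Section 6.1, the benchmarks as printed, no tumor-size weighting and complete 2-year follow-up. The plan should be corrected before analysis; the design does not need to change.

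**What to change.** 1. Define i as the lesion, nested in patient, and correct the wording in Sections 6.4 and 6.4.1 to 6.4.4 accordingly.
2. Pre-specify an interval and test for the 2-year q_RFA that account for patient clustering. One example is a patient-clustered variance with a small-sample correction and limits on the logit scale. The form chosen must use incomplete follow-up and stay defined when a 6-month interval has no recurrences. Step 5 tested only a single proportion with complete follow-up, so check the level of the actual procedure by simulation before analysis. Adding one common patient intercept to every category in Section 6.4.2 would not help, because it cancels between numerator and denominator.
3. Report the planned posterior alongside, with a note that it assumes independent lesions.
4. If the Rasch model is used, state how two lesions of one subject enter it.
5. Add a one-lesion-per-patient analysis for both outcomes, as descriptive sensitivity only; its power is about 0.61 and 0.67.
6. Restate power over rho 0 to 0.5 in place of a flat 80%.

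Cost: no new patients or data, some wording and analysis work, slightly wider intervals and lower stated power. With the recurrence level held below 5%, power is about 0.67 to 0.77 in the complete-follow-up check. About 0.03 is lost even at rho 0 (0.775 against 0.801).

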6.2 Statistical Design

A single-arm trial of the research PGP computer technology is proposed in which a comparison of outcomes is made to benchmarks based on prior studies. There are two primary outcomes, technical success and clinical success. Because the measurement process is drastically different for these outcomes, the statistical analysis also differs markedly for each outcome and so each is separately described. Results from Kim, et al. [5] provide the benchmark against which the *technical* success of PGP is assessed. Results from Mulier, et al. [4] provide the benchmark against which the *clinical* success of PGP is assessed. We will recruit patients with a tumor size $>2\text{cm}$, and we will categorize tumor size as small if $< 3\text{cm}$, medium if between 3cm and 5cm , and large if $> 5\text{cm}$. In our analyses for clinical outcomes, we will weight our sample to equate to the relative frequencies of small, medium and large tumors to ensure that the new trial data is relevant to the benchmark from the historical data [4]. In addition to performing overall analyses and statistical tests, we will also report estimates broken down by tumor size and other subgroups of interest.

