6.4 Statistical analysis of clinical success

It has been noted in the literature that if a tumor reoccurs in the same site, it typically does so within the first two years [4]. There is some evidence of reoccurrence as far out as 40 months but that is based on limited data and beyond 4 years there is no follow-up data [4]. For the purpose of this study, the analysis of the clinical outcome will be based on a 2-year endpoint. As with the determination of technical success,

a literature-based benchmark will be used in lieu of a concurrent control. Results in [5] suggest that the cumulative incidence of reoccurrence by 2 years is around 26.4% and by 4-years is around 37.8%. However, these results were not stratified by tumor size, which is known to be a very strong predictor of clinical success. In [4], reoccurrence rates of 14.1%, 24.5%, and 58.1% were reported for the small, medium and large tumor groups. However, these rates were evaluated over variable lengths of follow-up. The proportion of cases expected in the small, medium, and large categories are 12.9%, 41.9%, and 45.2% respectively (based on past clinical experience). The benchmark number to be used for the overall group comparison is the weighted average of these proportions with the above recurrence rates, which equals 24.1%. Because the failure rate data in [4] involve 1817 observations, we use this number as a basis for quantifying the precision in the baseline. Computing the lower end-point of a 95% confidence interval, we obtain $q_{\text{base}} = 0.2217$ as our ideal or most conservative benchmark against which to compare outcomes under PGP. This value is conservative even beyond the buffer provided by the allowance for uncertainty in its true value via the confidence interval end-point calculation as the follow-up times in [4] were shorter on average than 2-years.

For both the conservative and less conservative benchmarks, the overall assessment of the clinical success of PGP will be evaluated using the hypothesis test:

$$H_0: q_{\text{RFA}} \geq q_{\text{base}} \text{ against the alternative } H_1: q_{\text{RFA}} < q_{\text{base}}$$

where q_{RFA} is the probability of reoccurrence by 2-years of follow-up.

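### The clinical-success test does not hold benchmark and estimate to one tumor-size mix, so it may be confounded by size in either direction; the printed mix does not reproduce the 24.1% benchmark.

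*SAP*

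**What the plan says.** SAP 6.2 makes clinical success one of two primary outcomes, tested in a single arm against a literature benchmark. For that outcome it states "we will weight our sample to equate to the relative frequencies of small, medium and large tumors". The stated purpose is relevance to the benchmark from the historical series cited as [4]. No target frequencies are given.

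SAP 6.4 builds the benchmark. It reports that "reoccurrence rates of 14.1%, 24.5%, and 58.1% were reported for the small, medium and large tumor groups", gives expected proportions of 12.9%, 41.9% and 45.2% from the clinic's past experience, and continues: "The benchmark number to be used for the overall group comparison is the weighted average of these proportions with the above recurrence rates". The result is stated as 24.1%. A lower 95% limit based on 1817 observations gives q_base = 0.2217.

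SAP 6.4.4 defines the trial's side: "We wish to average the 2-year survival probability across the study patients". The formula is q_RFA = 1 − (1/n) Σ θ_i4, with n = 62 lesions (6.4.1) and no weights. The section then says that the mean size in [4], or size-group means, can or may be substituted for x_i, and that size-specific probabilities may be estimated. No section names the primary version.

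**The concern.** With no concurrent control, the size mix acts directly on the result. SAP 6.4 itself describes size as a very strong predictor, and the historical rates differ about fourfold between small and large tumors. If the benchmark assumes one mix and the estimate reflects another, the difference in mix is read as a device effect. A trial with fewer large tumors than the benchmark assumes favours the device; one with more can hide a real benefit. The margin meant to make the benchmark conservative is only about 2 percentage points (24.1% to 22.17%), so a moderate difference in mix can exceed it.

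**Working it through.** **Inputs.** Historical rates by size: 0.141, 0.245, 0.581 (SAP 6.4). Printed weights: 0.129, 0.419, 0.452 (6.4). Historical observations: 1817 (6.4). Lesions: 62 (6.1). One-sided level 0.05, and 80% power at a recurrence rate of 0.105 (6.4.6). All mixes below are small/medium/large.

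**Step 1: the benchmark.** Formula: Σ weight × rate.
- Weights as printed: 0.129 × 0.141 + 0.419 × 0.245 + 0.452 × 0.581 = 0.0182 + 0.1027 + 0.2626 = 0.383. This is not the stated 24.1%.
- Small and large weights exchanged: 0.452 × 0.141 + 0.419 × 0.245 + 0.129 × 0.581 = 0.0637 + 0.1027 + 0.0749 = 0.2413.
- Lower limit at the exchanged weights: 0.2413 − 1.96 × √(0.2413 × 0.7587 / 1817) = 0.2413 − 0.0197, about 0.222. With unrounded inputs it is 0.2217, as stated.

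Of the six ways to assign the three weights, only the exchanged one gives both 24.1% and 0.2217.

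**Step 2: the decision rule.** The exact one-sample binomial test of 0.2217 with n = 62 rejects at 8 or fewer recurrences: P(X ≤ 8 | 0.2217) = 0.048, and P(X ≤ 8 | 0.105) = 0.801. This reproduces the power statement in 6.4.6.

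**Step 3: can the model adjust for size?** SAP 6.4.2 sets log λ_ik = γ_k + βx_i with the same β for all five categories. Then

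θ_i4 = exp(γ_4 + βx_i) / Σ_k exp(γ_k + βx_i) = exp(γ_4) / Σ_k exp(γ_k).

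The factor exp(βx_i) is in every term and cancels. θ_i4 is the same for every lesion, whatever its size. Substituting another x_i, or weighting the average of θ_i4, leaves q_RFA unchanged. Size-specific probabilities from this model would all be equal.

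**Step 4: a device with no effect.** Assume the rates in [4] apply within each size group. Expected recurrence is Σ mix × rate, and false success is P(X ≤ 8 | 62, that rate). Mixes marked * are assumptions.

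| Mix | Expected recurrence | False success |
|---|---|---|
| 12.9/41.9/45.2 (printed) | 38.3% | under 0.01% |
| 45.2/41.9/12.9 (exchanged) | 24.1% | 2.2% |
| 50/40/10* | 22.7% | 4.0% |
| 55/38/7* | 21.1% | 7.1% |
| 60/35/5* | 19.9% | 10.6% |

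**Step 5: a device that works.** Take the risk ratio that gives 80% power at the exchanged mix, 0.105 / 0.2413 = 0.435, and apply it to each mix.

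| Mix | Recurrence with device | Power |
|---|---|---|
| 45.2/41.9/12.9 (exchanged) | 10.5% | 80% |
| 40/42/18* | 11.5% | 72% |
| 35/45/20* | 12.0% | 68% |
| 12.9/41.9/45.2 (printed) | 16.7% | 27% |

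**The case against.** A reader might infer that 6.2 weights the trial to the mix in [4] while 6.4 weights [4] to the clinic's mix, so that the two are swapped and the sides can never agree. The documents do not support that. Section 6.2 names no target, and the mix in [4] is not given. The only overall clinical benchmark that is tested is the one in 6.4, so weighting the sample to that benchmark's mix is a fair reading, and on it the two sides would agree. They would also agree under the unweighted formula if enrolment matched the benchmark mix. What stands is that the 6.4.4 formula does not carry out the promised weighting on either reading, and a match by enrolment would be luck: the plan sets no size quotas.

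Section 6.4.4 does address size, through the substitutions and the size-specific estimates. These are optional, and Step 3 shows that they have no effect in the model as written.

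The illustration has limits. The binomial rule is the SAP's stand-in, not its planned Bayesian test. The starred mixes have no source, and the cases above 5% cut large tumors from about 13% to 7% or less; the milder 50/40/10 stays below 5%. A reader might also infer that the main danger is a useless device passing. That presumes the exchanged mix is the true expectation. If the printed mix is right, the danger is the reverse: a real effect is missed.

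**Conclusion.** The concern holds in this form: the SAP states three size rules for one primary comparison, does not reconcile them, and names no primary version. Confounding by size is possible in either direction and depends on the enrolled mix; it is not certain. For a device with no effect, chance success runs from under 0.01% to 10.6% over the mixes shown; for a fixed relative effect, power runs from 80% down to 27%. These figures assume the size-specific rates in [4], independent lesions and the exact binomial rule.

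The arithmetic discrepancy is certain. The printed weights and the 24.1% cannot both be right, and the documents do not show which is wrong. If the printed weights are right, the benchmark is 38.3%, its lower limit on 1817 observations is 0.361, the rule becomes at most 15 of 62, and 80% power is reached at a recurrence rate of about 0.207.

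**What to change.** 1. Check the size weights in 6.4 against the clinic's records, and correct either the weights or the benchmark and power figures.
2. Replace the forecast mix by the observed one. Set the benchmark to Σ n_s r_s / n, where n_s is the trial's lesion count in size group s, r_s is the rate for that group in [4], and n = Σ n_s. Fix it before outcomes are read.
3. Use its lower 95% limit as q_base, with variance Σ (n_s/n)² r_s(1 − r_s)/N_s, where N_s is the group size in [4]. The documents give only the total of 1817, so the sponsor must take N_s from the source.
4. Keep q_RFA unweighted, delete the weighting in 6.2, and name this as the primary version.

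If the sponsor prefers to weight q_RFA to a stated mix, the benchmark must use the same mix, and the outcome model must change first: either the size effect differs by category, or the continuation-ratio form in 6.4.5 is used with size included.

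The main route costs SAP wording, a few lines of code and one look-up in the source; size is already part of the plan's data. The drawback is that the threshold is known only once the size mix is known, so the power in 6.4.6 becomes conditional on that mix.
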